6.2. Enrollment

6.2.1. Cycle 1 (Enrollment)

To be performed after the subject is determined to meet all eligibility criteria:

• Subject enrollment (can be done up to 3 days prior to C1D1)

6.3. Treatment Period

6.3.1. Cycle 1, Day 1 (C1D1; Week 1)

Before any invasive procedures, the following parameters are to be recorded:

- PROMIS Physical Function Scale
- EQ-5D-5L
- Vital signs including BP, pulse rate, and temperature
- 12-lead ECG

To be performed before the first morning dose of study drug:

- Assessment of concomitant medications including analgesics
- Clinical laboratory tests (only need to be done if they were not done within 72 hours of Day 1): serum chemistry, hematology, coagulation, hormone testing, liver function, and urinalysis
- Blood sampling for PK and PDy analysis
- Dispense study drug bottles

To be performed after the subject is dosed at the site:

• Record the dose (subject diary, source records, eCRF)

- 12-lead ECG to be performed 2 hours \pm 10 minutes after dosing
- AE assessment

6.3.2. Cycle 1, Day 8 (C1D8 Week 2) ± 2 days

The following parameters are to be recorded:

- Concomitant medications
- Clinical laboratory tests: liver function
- AE assessment

6.3.3. Cycle 1, Day 15 (C1D15 Week 3) ± 2 days

Before any invasive procedures, the following parameters are to be recorded:

- Vital signs, including BP, pulse rate, and temperature
- 12-lead ECG

To be performed before the morning dose:

- Assessment of concomitant medications including analgesics
- Treatment compliance assessment
- Clinical laboratory tests: liver function, hematology
- Blood sampling for PK and PDy analysis

To be performed after the subject is dosed at the site:

- Record of the dose (subject diary, source records, eCRF)
- Blood sampling for PK analysis at various postdose time points (see Section 8.2)
- 12-lead ECG to be performed 2 hours \pm 10 minutes after dosing
- AE assessment

6.3.4. Cycle 1, Day 22 (C1D22; Week 4) ± 2 days

The following parameters are to be recorded:

- Concomitant medications
- Clinical laboratory tests: liver function
- AE assessment

6.3.5. Cycle 2, Day 1 (C2D1; Week 5) ± 2 days

Before any invasive procedures, the following parameters are to be recorded:

• Vital signs including BP, pulse rate, and temperature

Other procedures to be performed:

- Treatment compliance assessment
- Assessment of concomitant medications including analgesics
- Physical examination
- Clinical laboratory tests: serum chemistry, hematology, liver function, serum pregnancy testing (as applicable)
- Blood sampling for PK and PDy analysis (see Section 8.2)
- Dispensation of study drug bottles
- AE assessment

6.3.6. Cycle 2, Day 8 (C2D8; Week 6) ± 2 days

The following parameters are to be recorded:

- Concomitant medications
- Clinical laboratory tests: liver function
- AE assessment

6.3.7. Cycle 2, Day 15 (C2D15; Week 7) ± 2 days

The following parameters are to be recorded:

- Concomitant medications
- Clinical laboratory tests: liver function
- AE assessment

6.3.8. Cycle 2, Day 22 (C2D22; Week 8) ± 2 days

The following parameters are to be recorded:

- Concomitant medications
- Clinical laboratory tests: liver function
- AE assessment

6.3.9. Cycle 3, Day 1 (C3D1; Week 9) ± 7 days

Before any invasive procedures, the following parameters are to be recorded:

- PROMIS Physical Function Scale
- EQ-5D-5L
- Vital signs including BP, pulse rate, and temperature

Other procedures to be performed:

- Treatment compliance assessment
- Assessment of concomitant medications including analgesics

- Clinical laboratory tests: serum chemistry, hematology, liver function, serum pregnancy testing (as applicable)
- Random postdose blood sampling for PK and PDy analysis
- Dispensation of study drug bottles
- AE assessment

6.3.10. Cycle 3, Day 15 (C3D15; Week 11) ± 7 days

The following parameters are to be recorded:

- Concomitant medications
- Clinical laboratory tests: liver function
- AE assessment

6.3.11. Cycle 4, Day 1 (C4D1; Week 13) ± 7 days

Before any invasive procedures, the following parameters are to be recorded:

• Vital signs, including BP, pulse rate, and temperature

To be performed within (\pm) 7 days of the visit:

- Treatment compliance assessment
- Assessment of concomitant medications including analgesics
- Physical examination
- MRI of the affected joint (with local assessment of progression status). The Investigator may request a centrally read blinded MRI to confirm progression, eg, if a subject's mid-study clinical profile or local radiological assessment indicates progression
- Photographic documentation of tumor
- Range-of-motion assessment of the affected joint

Other procedures to be performed:

- Clinical laboratory tests: serum chemistry, hematology, liver function, serum pregnancy testing (as applicable), and urinalysis
- Dispensation of study drug bottles
- AE assessment

6.3.12. Cycle 5, Day 1 (C5D1; Week 17) ± 7 days

Before any invasive procedures, the following parameters are to be recorded:

- PROMIS Physical Function Scale
- EQ-5D-5L

• Vital signs including BP, pulse rate, and temperature

Other procedures to be performed:

- Treatment compliance assessment
- Assessment of concomitant medications including analgesics
- Clinical laboratory tests: serum chemistry, hematology, liver function, serum pregnancy testing (as applicable)
- Random postdose blood sampling for PK and PDy analysis
- Dispensation of study drug bottles
- AE assessment

6.3.13. Cycle 6, Day 1 (C6D1; Week 21) ± 7 days

Before any invasive procedures, the following parameters are to be recorded:

• Vital signs including BP, pulse rate, and temperature

Other procedures to be performed:

- Treatment compliance assessment
- Assessment of concomitant medications including analgesics
- Clinical laboratory tests: serum chemistry, hematology, liver function, serum pregnancy testing (if applicable)
- Dispensation of study drug bottles
- AE assessment

6.3.14. Cycle 7, Day 1 Visit (C7D1; Week 25) ± 7 days

Before any invasive procedures, the following procedures have to be performed:

- PROMIS Physical Function Scale
- EQ-5D-5L
- Vital signs including BP, pulse rate, and temperature
- 12-lead ECG

To be performed within (\pm) 7 days of the visit:

- Treatment compliance assessment
- Assessment of concomitant medications including analgesics
- Surgical Assessment Questionnaire
- Weight
- Physical examination

- MRI of the affected joint (with local assessment of progression status). The Investigator may request a centrally read blinded MRI to confirm progression, eg, if a subject's mid-study clinical profile or local radiological assessment indicates progression
- Photographic documentation of tumor
- Range-of-motion assessment of the affected joint

Other procedures to be performed:

- Clinical laboratory tests: serum chemistry, hematology, coagulation, liver function, hormone testing, serum pregnancy testing (as applicable), and urinalysis
- AE assessment

The following procedures will be performed as part of the C7D1visit if the subject will continue the study:

After the subject is dosed at the site:

- Record the dose (subject diary, source records, eCRF)
- Dispensation of study drug bottles

6.3.15. Cycle 10+, Day 1 (C10+D1; Week 37+) ± 7 days

To be performed at C10+D1 \pm 7 day and every 12 weeks thereafter (eg, C13, C16, C19).

Before any invasive procedures, the following parameters are to be recorded:

- PROMIS Physical Function Scale
- EQ-5D-5L
- Vital signs, including BP, pulse rate, and temperature

To be performed within (\pm) 7 days of the visit:

- Physical examination
- Treatment compliance assessment
- Assessment of concomitant medications, including analgesics
- MRI of the affected joint (with local assessment of progression status). The Investigator may request a centrally read blinded MRI to confirm progression, eg, if a subject's mid-study clinical profile or local radiological assessment indicates progression
- Photographic documentation of tumor
- Range-of-motion assessment of the affected joint

To be performed other procedures:

• Clinical laboratory tests: serum chemistry, hematology, liver function, serum pregnancy testing (if applicable)

- Dispensation of study drug bottles
- AE assessment

6.3.16. Post-treatment Visit (last dose + 28 days) \pm 7 days

To be performed at 28 ± 7 days after the last dose of study drug.

Before any invasive procedures, the following parameters are to be recorded:

- PROMIS Physical Function Scale
- EQ-5D-5L
- Vital signs including BP, pulse rate, and temperature
- 12-lead ECG

The following procedures are to be performed within (\pm) 7 days of this visit:

- Assessment of concomitant medications including analgesics
- Surgical Assessment Questionnaire
- Weight
- Physical examination
- MRI of the affected joint (for subjects who withdraw from the study for reasons other than progression; local assessment of progression status will be recorded)
- Photographic documentation of tumor
- Third-party range-of-motion assessment of the affected joint

Other procedures to be performed:

- Clinical laboratory tests: serum chemistry, hematology, coagulation, liver function, hormone testing, serum pregnancy testing (if applicable), and urinalysis
- If surgical resection of the tumor is performed within 28 days after the last dose of study drug, obtain details and outcome of the surgery
- AE assessment
- For subjects terminating the study because of progression, document if they plan to undergo any new TGCT therapy, including surgery, during the 28 days period (± 7 days) after their last dose of study drug

6.3.17. End-of-Study or Early Termination Visit (last dose + 12 weeks) ± 7 days

This visit is scheduled 12 weeks \pm 7 days after the last dose of study drug or before any new TGCT therapy, including surgery, whichever occurs first. It is scheduled for subjects who withdraw from the study for reasons other than progression.

• Concomitant medications

- If surgical resection of the tumor is performed within 12 weeks after the last dose of study drug, obtain details and outcome of the surgery
- MRI of the affected joint (with local assessment of progression status) is to be performed within (±) 7 days of the visit
- Photographic documentation of tumor
- Assess if the subject plans to begin any new TGCT therapy, including surgery
- Clinical laboratory tests: serum pregnancy testing (if applicable)
- AE assessment
- Terminate the subject from the study

6.3.18. Long Term Follow-up (every 6 months after end-of-study or early termination visit) ± 2 weeks

After completion of the end-of-study or early termination visit, the long term follow-up will be performed every 6 months by telephone contact. The questionnaire is provided in Section 16.5.

• Subject status

7. EFFICACY ASSESSMENTS

Subjects will be assessed for the efficacy endpoints listed in Section 3.1.2

7.1. Primary Efficacy Endpoint

The primary endpoint will be the proportion of subjects who achieve a CR or PR of pexidartinib based on RECIST 1.1 at Week 25 by centrally reviewed MRI scan.

The RECIST 1.1 response categories are defined by the following criteria:

- Complete Response (CR) Disappearance of all tumors.
- **Partial Response (PR)** At least a 30% decrease in the sum of diameters of target tumors, taking as reference the baseline sum diameters.
- **Progressive Disease (PD)** At least a 20% increase in the sum of diameters of target tumors, using the smallest sum on study as the reference. In addition to the relative increase of 20%, the sum must also demonstrate an absolute increase of at least 5 mm. The appearance of one or more new tumors is also considered progression.
- **Stable Disease (SD)** Neither sufficient shrinkage to qualify for PR nor sufficient increase to qualify for PD.

CR and PR will define response for the primary endpoint and additional efficacy analyses.

Determination of an overall response for each time point is based on the combination of responses for target lesions, and the presence or absence of one or more new lesions. For the purpose of this protocol and in alignment with RECIST 1.1, determination of the tumor response status for each subject within 24 weeks treatment with respect to the primary efficacy endpoint is shown in Table 7.1.

To be considered a response, a tumor must meet the criteria for response and must have documented non-progression at Week 25. A tumor that achieves PR at Week 13 followed by neither sufficient shrinkage to qualify for CR nor sufficient increase to qualify for PD (ie, non-CR/non-PD/not evaluable [NE]) at Week 25 will be considered a responder for the primary efficacy endpoint.

Time Point Response at Week 13 (C4D1 visit)	Time Point Response at Week 25 (C7D1visit)	Tumor Response Status (Primary efficacy endpoint)
CR or PR	CR	Response (CR)
CR or PR	PD	Nonresponse (PD)
PR	non-CR/non-PD/non-NE ^a	Response (PR) ^b
SD	CR or PR	Response (CR or PR)
SD	SD	Nonresponse (SD)
SD	PD	Nonresponse (PD) ^c
CR, PR, SD, or NE	NE	Nonresponse (NE)
PD	Any	Nonresponse (PD)
NE	CR or PR	Response (CR or PR)
NE	SD or PD	Nonresponse (SD or PD)

 Table 7.1:
 Definitions of Response for the Primary Endpoint

CR = complete response; NE = not evaluable; PD = progressive disease; PR = partial response;

SD = stable disease

^a Neither sufficient shrinkage to qualify for CR nor sufficient increase to qualify for PD, taking as reference the nadir at Week 13.

^b A tumor that has achieved the criteria of PR will be considered an ongoing PR until progressive disease is objectively documented.

^c To be considered SD, the tumor must achieve the criteria for SD at the Week 25 visit; shorter-duration SD will not be considered SD at the end of Week 24.

For the entire study, centralized review of the MRI scans will be performed by readers blinded to study subject information according to procedures outlined in a separate MRI Imaging Charter. Scans will be obtained according to the MRI Imaging Charter. The Imaging Charter for this study describes the image acquisition standards and methodology to be used as well as the standards for image interpretation.

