7.1.1. Tumor Imaging

MRI (Noncontrast or follow the standard operation of the sites) of the affected joint will be performed at the study visits indicated in the Schedule of Assessment (Table 16.3). All MRI scans will be centrally read. Local evaluation of radiological response, stable disease (SD) or PD according to RECIST 1.1 will be recorded in the eCRF. The central MRI assessment report of progression status will not be provided unless requested. The Investigator will follow procedures (including instructions on proper imaging technique, and labeling) outlined in a separate MRI Procedure Manual. The results of the baseline, centrally read MRI scan will be used to qualify a subject, and all subsequent MRI scans will be read centrally.

If disease progression is indicated clinically or by local radiological assessment according to RECIST 1.1 at or after Week 13 but before Week 25, the Investigator may request a central review for evaluation of disease progression. If a central reading confirms RECIST 1.1 defined

disease progression, subject will be discontinued from the study unless the Investigator and the DS's Medical Monitor judge that the subject would potentially benefit from continued treatment with pexidartinib.

During the study, if indicated, Investigators should request confirmation of radiological disease progression by central read. Otherwise, central reading of MRI scans may be performed during or after the subject has completed the study. Details for MRI scan reads are outlined in the MRI Procedure Manual.

Subjects who terminate the study because of radiological disease progression will NOT have a follow-up MRI at their post-treatment visit.

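### Table 7.1 has no row for progression read centrally between Week 13 and Week 25, so a subject kept on treatment after it can still be scored a primary-endpoint responder

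*Combined protocol and SAP*

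**What the plan says.** Protocol Section 7.1 defines PR as at least a 30% fall in the sum of diameters, "taking as reference the baseline sum diameters". PD is at least a 20% and 5 mm rise, "using the smallest sum on study as the reference", or a new tumor. For a response, "a tumor must meet the criteria for response and must have documented non-progression at Week 25".

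Table 7.1 then gives the status from two inputs, the Week 13 and the Week 25 time-point responses. The rows that matter here are:
- Week 13 PD, Week 25 anything: nonresponse (PD).
- Week 13 SD or NE, Week 25 CR or PR: response.
- Week 13 CR or PR, Week 25 CR: response (CR).
- Week 13 PR, Week 25 evaluable and neither CR nor PD: response (PR). The text of Section 7.1 also calls a tumor with PR at Week 13 and neither CR nor PD at Week 25 a responder.

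Two footnotes qualify the last row. Footnote a defines the Week 25 category "taking as reference the nadir at Week 13". Footnote b reads: "A tumor that has achieved the criteria of PR will be considered an ongoing PR until progressive disease is objectively documented".

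MRI is scheduled every 12 weeks (Sections 1.4 and 16.6), with none between Weeks 13 and 25. Section 7.1.1 nevertheless provides for this case, which it words as "If disease progression is indicated clinically or by local radiological assessment according to RECIST 1.1 at or after Week 13 but before Week 25". A central read can then be asked for. The Synopsis goes further and requires central verification of any progression before Week 25. If PD is confirmed, the "subject will be discontinued from the study unless the Investigator and the" sponsor's Medical Monitor expect a benefit from continuing. Section 7.1.1 also says that all MRI scans are read centrally. Section 10.2 makes a subject without a Week 25 MRI a nonresponder and says nothing about PD followed by an evaluable Week 25 scan.

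**The concern.** A centrally read PD between the two visits is not an input to Table 7.1. Followed exactly, some rows give a responder status to a subject whose progression has been centrally confirmed, while the same finding at Week 13 makes the subject a nonresponder regardless of what follows.

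At stake is the primary endpoint of an open-label, single-arm trial of about 35 subjects. A subject with interim PD who is withdrawn has no Week 25 MRI and is a nonresponder under Section 10.2. A subject with the same PD who is continued keeps the possibility of being scored a responder. For subjects with interim PD, the choice made by the Investigator and the sponsor's Medical Monitor can therefore leave the ORR unchanged or raise it, but cannot lower it.

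**Working it through.** **The plan's own figures.** Section 10.11 lists 95% intervals for 9 to 16 responders out of 35, and Section 10.5.1 names the Clopper-Pearson method. With x responders out of n, the lower limit is the 0.025 quantile of Beta(x, n − x + 1) and the upper limit is the 0.975 quantile of Beta(x + 1, n − x). With n = 35, all eight rows reproduce to 0.1 point, for example 13/35 = 37.1% (21.5%, 55.1%).

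**Table 7.1 applied to sequences with an interim scan.** The sums in mm are assumed for illustration. PR is tested against baseline, PD against the smallest sum so far.

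| Baseline / Week 13 / interim / Week 25 | Week 13 | Interim | Week 25 | Table 7.1 |
|---|---|---|---|---|
| 60 / 50 / 64 / 42 | −16.7%: SD | 64 vs 50: +28%, +14 mm: PD | 42 vs 60: −30%: PR | Response |
| 100 / NE / 125 / 65 | NE | 125 vs 100: +25%, +25 mm: PD | 65 vs 100: −35%: PR | Response |
| 100 / 60 / 75 / 0 | −40%: PR | 75 vs 60: +25%, +15 mm: PD | 0: CR | Response (CR) |
| 60 / 40 / 50 / 47 | −33.3%: PR | 50 vs 40: +25%, +10 mm: PD | 47 vs 40: +17.5%: not PD | Row: Response (PR); footnote b: PR has ended |
| 100 / 85 / 105 / 100 | −15%: SD | 105 vs 85: +23.5%, +20 mm: PD | 100 vs 85: +17.6%: SD | Nonresponse |

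The first three sequences are scored as responses, and no footnote reaches those rows. In the fourth, footnote b ends the PR at the interim PD, while the row and the sentence in Section 7.1 say responder. The fifth is a nonresponse in any case.

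**Footnote a.** The Week 13 PR row implies a Week 13 sum at least 30% below baseline. On scheduled scans, that is the smallest sum before Week 25, so footnote a and the PD definition use the same reference. They part only if an unscheduled scan is smaller still. For 60 / 40 / 30 / 45, Week 25 is 45/40 = +12.5% under footnote a (not PD), but 45/30 = +50% and +15 mm under the PD definition (PD).

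**Size.** One subject is 1/35 = 2.9 points. The documents give no count of such subjects, so 0 to 3 is an assumed range, starting from 13 scored responders:

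| Reclassified | ORR (95% CI) |
|---|---|
| 0 | 13/35 = 37.1% (21.5%, 55.1%) |
| 1 | 12/35 = 34.3% (19.1%, 52.2%) |
| 2 | 11/35 = 31.4% (16.9%, 49.3%) |
| 3 | 10/35 = 28.6% (14.6%, 46.3%) |

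**The case against.** Four points can be made for the plan.

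- **Footnote b settles the most direct path.** It is part of the table and is not limited to the two visits, so PR at Week 13, interim PD, then non-PD at Week 25 need not be a response. This stands. A reader might infer that Table 7.1 ignores interim PD throughout, and footnote b shows that it does not. What remains on this path is a conflict of wording with the row and with Section 7.1.
- **No interim MRI is planned.** Section 7.1.1 ties MRI to the scheduled visits, and its clause can be read as asking for an early central read of the Week 13 scan, where PD is already covered. This stands in part: the documents set out no procedure for unscheduled MRI. But progression that arises after the Week 13 scan, which the clause includes, can be confirmed centrally only from a further scan.
- **Continuing earns nothing by itself.** On the open rows, Week 25 must still show CR or at least 30% shrinkage from baseline, read by central readers blinded to subject information. In the 60 / 50 / 64 / 42 sequence the tumor must fall by 34% (64 to 42 mm) after PD. This stands and makes such cases uncommon.
- **The Imaging Charter or MRI Procedure Manual may hold a rule for unscheduled reads.** They are not among the documents. Such a rule cannot be assumed to override a stated row of the primary-endpoint table.

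**Conclusion.** The gap is real but narrow. It is open on three routes: SD then CR or PR, NE then CR or PR, and CR or PR then CR, each with centrally read PD in between. There the stated rows return a status that conflicts with the table's own treatment of PD at Week 13. This is therefore more than a missing detail.

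It rests on three assumptions: an unscheduled MRI is done, PD on it is read centrally, and treatment continues. The number of such subjects cannot be derived from the documents and is probably small or zero. Each is worth 2.9 points of ORR if all 35 planned subjects are in the full analysis set.

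Two stronger readings are not supported. A reader might infer that the reported ORR will be materially inflated, but nothing in the documents shows that any such case will occur. A reader might also take footnote a as an error in the scheduled assessments, but it agrees with the PD definition unless an unscheduled scan falls below the Week 13 sum.

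**What to change.** - **Table 7.1:** replace the row for PD at Week 13 with one reading: *PD by central read at any MRI, scheduled or unscheduled, before the Week 25 MRI / Any / Nonresponse (PD)*.
- **Section 7.1 text:** in the sentence on PR at Week 13, add that no PD has been read centrally before the Week 25 MRI, so that the sentence, the row and footnote b agree.
- **TVS and SSD:** apply the same rule to both response statuses, since Sections 7.2 and 3.1.2.3 determine them in a way similar to the primary endpoint.
- **Footnote a (minor consistency edit):** replace the reference to the Week 13 nadir with the smallest sum on study, as in the PD definition.

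The cost is one table row, one sentence and one footnote. No new scans or reads are needed, because all MRI scans are already read centrally. Section 14.4 allows a change in planned analysis to be documented in an amendment or the SAP, and Section 10.12 has the SAP finalised before database lock. The downside is that the ORR may be slightly less favourable. The change concerns endpoint scoring only and takes no position on whether a subject should continue treatment.
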